1.2 Study Product Profile

1.2.1 Drug Profile

QM1114 is a protein dimer of 150 kilodalton (kDa)	
CCI	
CCI	
CCI	Unlike other

commercially available BoNTs, QM1114 is manufactured and formulated without any animal or human proteins, thereby reducing the potential risk of viral contamination in the product.

```
CCI
```

1.2.2 Pre-Clinical Documentation

The pre-clinical pharmacology-toxicology program has included appropriate toxicology studies to support safety for administration of QM1114-DP at the proposed dose of 50 unit (U), 60 U, and combined total dose of 110 U which will be evaluated in this study.

```
CCI
```

No safety pharmacology or pharmacokinetic studies were conducted for QM1114-DP since no systemic exposure to the product is expected with a single IM administration to specific facial muscles using the dose proposed. Additionally, BoNT-A binds with high affinity at the neuronal synapses at the local injection site. ¹¹ Therefore, any metabolism and elimination of the product would occur at the local site of injection.

CCI		
CCI		
CCI		

..

>

GALDERMA

Title
43QM1903 Clinical Study Protocol - QM1114 - LTS for LCL/GL

MA-40372

[figure not shown]

1.2.3 Clinical Documentation

Dec id

8-26 19:44

43QM1903 Clinical Study Protocol - QM1114 - LTS for LCL/GL

MA-40372

CCI

CTN 43QM1313

Following successful completion of clinical study placebo controlled, dose finding study of QM1114-DP using three different single doses of QM1114-DP (30, 45, 60 U) in male or female subjects aged over 18 years with moderate to very severe GL was performed.

CCI		
CCI		
CCI		
CCI		
CCI		

	Title	Doe id
♣ GALDERMA	43QM1903 Clinical Study Protocol - QM1114 - LTS for LCL/GL	MA-40372

[figure not shown]
CCI	
CCI	
CCI	
CCI	

1.2.4 Dose Rationale

Non-clinical studies have shown a similarity between QM1114-DP potency units and Speywood units (Dysport®). Both safety and efficacy for the 30-60 U dose range of QM1114-DP were established in the phase 2 study (study CTN 43QM1313). In the treatment of GL with Speywood unit products (Dysport®/Azzalure®), the recommended dose is 50 U. Based on the evaluation of results for the different dose levels studied to date in the clinical program of QM1114-DP, the Sponsor has concluded that a 50 unit dose offers an appropriate balance between efficacy, duration of effect and safety.

For treatment of the LCL and GL, alone or in combination, both the safety and efficacy of QM1114-DP was established in the phase 1 study the 60 U dose has been selected for further clinical development, and for treatment in the GL the 50 U dose has been selected. For the combined LCL and GL treatment, QM1114-DP was evaluated at two ascending dose levels (i.e., 110 U [50 U in the GL and 60 U in the LCL], and 140 U [50 U in the GL and 90 U in the LCL). The 110 U dose has been selected for further clinical development in the treatment of LCL and GL. This is consistent with the combined recommended Speywood unit doses in each treatment area as well as clinical experience, as specified above.

1.3 Risk/Benefit Assessment

The risk of AEs occurring is reduced by using physicians who are experienced in the botulinum toxin injection technique. All treating Investigators will be trained in the administration technique of QM1114-DP prior to the study start.

The benefit to subjects receiving QM1114-DP in this study will be a temporary reduction in the appearance of their GL and LCL, and additional treatments throughout the study when eligible.

No additional risks specific of the 110 U dose of QM1114-DP (50 U in the GL, 60 U in the LCL) are anticipated, and sufficient clinical experience with BoNT-A products with similar mode of

action for facial aesthetic use at dose levels corresponding to the dose levels in this study demonstrate the potential benefit of the proposed treatments. Adverse events will be recorded at each study visit, and subjects will also be queried for any potential signs and symptoms of local and distant spread of the toxin effect.

In conclusion, given the anticipated low level of transient and acceptable risks, the risk/benefit assessment of the use of QM1114-DP for the long-term treatment of moderate to severe GL and LCL, and appears to offer a substantial clinical benefit at reasonable risk.

2. CLINICAL STUDY OBJECTIVES, ENDPOINTS, AND CLINICAL HYPOTHESIS

2.1 Clinical Study Objectives

The objective of this study is to evaluate the safety and efficacy of repeated injections of QM1114-DP for the treatment of moderate to severe GL and LCL.

2.1.1 Primary Objectives and Endpoints

The primary objective of this study is to evaluate the safety of repeated injections of QM1114-DP for the treatment of moderate to severe GL and LCL.

Primary endpoints include:

- Incidence and severity of treatment emergent AEs (TEAEs)
- Focused physical examination (FPE) findings

[figure not shown]
2.1.2 Secondary Objectives and Endpoints

The secondary objectives and endpoints of the study are:

 Objective: To evaluate the efficacy of repeated injections of QM1114-DP for the treatment of moderate to severe GL and LCL.

Endpoints:

- Percentage of subjects who achieve grade/level 0 or 1 at each visit in each treatment cycle using the
 - o GL-ILA 4-point Photographic Scale at maximum frown
 - o LCL-ILA 4-point Photographic Scale at maximum smile

- Percentage of subjects who achieve ≥1 grade/level improvement from baseline at each visit in each treatment cycle using the
 - o GL-ILA 4-point Photographic Scale at rest

GALDERMA Title 43QM1903 Clinical Study Protocol - QM1114 - LTS for LCL/GL MA	MA-40372
--	----------

	0	LCL-ILA 4-point Photographic Scale at relaxed position
CCI		
CCI		
CCI		
CCI		
001		
CCI		
CCI		
CCI		
CCI		

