	(SOC) and preferred term (PT) assigned to the event using MedDRA, both
	for the whole study and per cycle.
	Graphs will be used as appropriate for visualization of the results.
	Proportion of responders on the photographic scales will be presented by
	treatment cycle.
	*
	CCI
Sample Size:	The cample size is not based on a statistical calculation and the calculat
Sample Size.	The sample size is not based on a statistical calculation and the selected number is regarded sufficient in order to appropriately capture safety
	information in an evaluation of QM1114-DP.
Interim Analysis (IA):	Not applicable. An interim analysis is not planned for this study.

CLINICAL STUDY FLOW CHART

Figure 1 Study Flow Chart

43QM1903 Clinical Study Protocol - QM1114 - LTS for LCL/GL

Doc id

MA-40372

SCHEDULE OF ASSESSMENTS

Table 1 Schedule of Assessments

Follow-up visit (every 4th week) windows are calculated from Baseline/Day 0.	Visit 11	Visit 21	Visit 2a	Visit 2b	Visit 3	Visit 4	Visit 5-12	Visit 5a-12a	Visit 5b-12b	Visit 13	Visit 14	Visit 15 EOS/ET ⁹
Post-treatment visits (Day 7 and Day 14) windows are calculated from date of current treatment cycle.	Screening	Baseline/ Day 0	Post-tr	eatment	Week 4	Week 8	Every 4th week ¹⁰	Performed on h	eatment rif re-treatment it 5-12	Week 44	Week 48	Week 52
		(within 2 weeks after screening)	Day 7 (±1 day)	Day 14 (±3 days)	(±5 days)	(±5 days)	(+5 days)	Day7 (±1 day)	Day 14 (±3 days)	(±5 days)	(±5 days)	(±5 days)
In formed Consent	X											
Demo graphic Data ² including Fitzpatrick skin type, medical history & concurrent diseases, previous facial treatments/procedures (toxin naïve/non-toxin naïve)	x											
Inclusion /Exclusion Criteria	X	X^3										
Concomitant Therapies/ Procedures	X	X ⁴	X	X	X	X	X ⁴	X	X	X	X	X
Adverse Events	X	X ⁴	X	X	X	X	X ⁴	X	X	X	X	X
Urine Pregnancy Test ⁵	X	X^3					X^3					X
Vital Signs ⁶		X ⁴	X	X	X	X	X ⁴	X	X	X	X	X
Blood sample clinical chemistry and hematology		X^3										X
Blood sample for serum antibody testing		X^3					X ¹¹			X^{11}		X
Glabellar Line Severity (GL-ILA)	X	X^3	X	X	X	X	X^3	X	X	X	X	X
Lateral Canthal Lines Severity (LCL-ILA)	X	X^3	X	X	X	X	X3	X	X	X	X	X
Focused Physical Examination (face, head, neck)	х	X3	х	х				х	х			х
Photography		X^3	X	X	X	X	X ³	X	X	X	X	X
Treatment		X^{7}										
Eligibility for re-treatment							X					
Re-treatment							X ⁷					

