In the early 1990s, patients treated with BoNT-A for blepharospasm were observed to lose their frown lines and, ^{5,9} since publishing these observations, the use of BoNT-A in the aesthetic setting has accelerated. Injectable BoNT-A products have been investigated for multiple aesthetic indications in attempts to reverse the appearance of aging, especially in the facial region.² In the treatment of facial lines, the effect of BoNT-A injections usually persists for approximately 4-6 months. Facial muscle activity and severity of the facial wrinkles then returns to baseline. Full functionality of facial muscles is usually restored by approximately 6 months post-treatment.¹⁰

There are four BoNT-A products currently licensed in the United States (US) for the treatment of GL (Botox Cosmetic[®], Dysport[®], Xeomin[®], and JeuveauTM), and one licensed for the treatment of LCL (Botox Cosmetic[®]). QM1114-DP is a novel botulinum toxin type-A1 which is presented as a liquid formulation. Unlike the main commercially available botulinum toxins in the US, QM1114-DP is manufactured and formulated without any animal or human proteins. As a novel BoNT-A with a differentiated formulation, QM1114-DP is being developed for the long-term treatment of moderate to severe GL and LCL in adults over 18 years.

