6.1.6.3 Treatment Regimen

Subjects will receive up to four treatments with QM1114-DP in their glabellar and lateral canthal lines during the study period, each treatment cycle is at least 12 weeks apart. Follow-up assessments for treated subjects are conducted at Day 7 and Day 14 post-treatment. All subjects are followed up every 4th week for a period of up to 52 weeks.

The following conditions are required to be met for re-treatment post-baseline:

- · It has been at least 12 weeks since the previous treatment in the intended area
- For GL re-treatment:
 - Moderate (grade 2) or severe (grade 3) rhytides at maximum frown as assessed by the Investigator (ILA).

CCI

- For LCL re-treatment:
 - Moderate (grade 2) or severe (grade 3) rhytides at maximum smile as assessed by the Investigator (ILA).

CC

- In order to treat LCL, both sides should meet severity criteria and be treated at the same visit.
- There are no ongoing adverse events assessed as related to the treatment, which could
 preclude the subject from re-treatment.
- Subject agrees to receive re-treatment.
- If subject is a female of child-bearing potential, agrees to take a pregnancy test and test result
 must be negative in order to receive re-treatment.
- There is no other medical or surgical condition that would put the subject at undue risk in case he/she receives an additional treatment cycle, according to investigator's judgment.

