9.1.3 Handling of Drop-Outs and Missing Data

No imputation of missing data will be performed.

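### Grade 0/1 response rates after cycle Week 12 lose subjects because they failed and were re-treated, and so overstate persistence of response

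*Protocol*

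**What the plan says.** - **Endpoint.** Section 2.1.2 lists "Percentage of subjects who achieve grade/level 0 or 1 at each visit in each treatment cycle using the" GL scale at maximum frown and LCL scale at maximum smile. A second visible pair is "Percentage of subjects who achieve ≥1 grade/level improvement from baseline at each visit in each treatment cycle using the" same scales at rest or relaxed. The Synopsis (Principal Statistical Method) adds: "Proportion of responders on the photographic scales will be presented by" treatment cycle.
- **How a new cycle starts.** Section 6.1.6.3 requires at least 12 weeks since the last treatment of the area and, for GL, "Moderate (grade 2) or severe (grade 3) rhytides at maximum frown as assessed by the Investigator (ILA"). The LCL rule is the same at maximum smile, with the addition: "In order to treat LCL, both sides should meet severity criteria and be treated at the same visit". The subject must also agree, and adverse-event, pregnancy-test and medical conditions must be met. Section 3 confines re-treatment to study Weeks 12 to 40.
- **Order of events.** Section 7.1.1 and Table 1 (footnote 3) place the severity grading before any re-treatment at the same visit.
- **Missing data and analysis set.** Section 9.1.3: "No imputation of missing data will be performed". Section 9.1.2.2 analyses efficacy on the FAS, which is defined once for the whole study. No section states the denominator for a given visit of a given cycle.

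**The concern.** Response is grade 0 or 1, and an area can be re-treated only at grade 2 or 3. A subject re-treated in an area has therefore just been recorded as a non-responder there (for LCL, on both sides). That subject's later visits belong to the next cycle. The earlier cycle has no further values for the subject, and Section 9.1.3 forbids supplying any.

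This is not random drop-out, because the outcome itself causes the exit. Table entries for cycle Weeks 16, 20, 24 and beyond would describe only subjects not yet re-treated. The clinical hypothesis in Section 2.2 concerns long-term use, so a reader would naturally take these figures as the share of treated subjects still responding. On an observed-case basis they are not that share.

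**Working it through.** The protocol gives no expected response rate, so there is no figure of its own to reproduce. What follows is an illustration.

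**Inputs.**
- Visits every 4 weeks, with re-treatment possible from cycle Week 12 (Sections 3 and 6.1.6.3).
- Duration: Section 1.1 says "the effect of BoNT-A injections usually persists for approximately 4-6 months", which is about 17.3 to 26 weeks, with 5 months = 21.7 weeks. This describes the toxin class, not this product's time to loss of grade 0/1.
- Assumed: normal response duration, SD 5 weeks; at each visit a share u of the relapsed subjects still in the cycle is re-treated, with u = 0, 0.5 or 1.

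**Formulas.** S(w) = share still at grade 0/1 at cycle Week w, over everyone treated in the cycle. N(w) = relapsed subjects still in the cycle when graded at Week w.

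- N(12) = 1 − S(12)
- N(w) = (1 − u) × N(w − 4) + S(w − 4) − S(w)
- Observed-case rate = S(w) / [S(w) + N(w)]

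**Mean 21.7 weeks.** S at Weeks 12, 16, 20, 24 is 97.4%, 87.3%, 63.3%, 32.3%.

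- u = 1: N(24) = 63.3 − 32.3 = 31.0; rate = 32.3 / 63.3 = 51.0%.
- u = 0.5: N runs 2.6, 11.4, 29.7, 45.8; rate = 32.3 / 78.1 = 41.3%.
- u = 0: N(24) = 67.7; rate = 32.3%, no excess.

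**Cycle Week 24 across the range of means**

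| Mean | All treated in cycle | Observed, u = 0.5 | Observed, u = 1 | Excess (points) |
|---|---|---|---|---|
| 17.3 wk (4 mo) | 9.1% | 17.1% | 30.7% | 8.0 to 21.6 |
| 21.7 wk (5 mo) | 32.3% | 41.3% | 51.0% | 9.0 to 18.7 |
| 26 wk (6 mo) | 65.5% | 70.0% | 74.1% | 4.5 to 8.6 |

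At cycle Week 16 the effect is smaller. With u = 1 it is 87.3% against 89.6% for a 5-month mean and 97.7% against 98.0% for 6 months. At cycle Week 12 it is zero, because grading precedes re-treatment.

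**A different shape.** With Weibull durations (shape 3), S(t) = 2^−(t/median)³. For a median of 20 weeks S(20) = 50% and S(24) = 30%, so with u = 1 the observed rate is 30 / 50 = 60%, and the denominator falls from 900 to about 450. Over medians of 16, 20 and 26 weeks and u from 0.5 to 1, the Week 24 excess is about 10 to 27, 16 to 30 and 13 to 21 points. The direction holds; the size depends on the shape.

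**Which cycles.** A cycle started at study Week s first allows re-treatment at s + 12, which must be no later than 40, so s ≤ 28. Starts at Weeks 32, 36 and 40 reach cycle Week 12 at study Weeks 44, 48 and 52, too late. A fourth cycle starts at Week 36 at the earliest and cannot be affected. The Week 24 figures above assume exits at cycle Weeks 12, 16 and 20, so they apply to starts with s + 20 ≤ 40, that is s ≤ 20. Later starts have fewer exits.

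**The case against.** **No denominator is written down.** A reader might infer that the protocol expressly removes relapsed subjects from the denominator. It does not. Section 9.1 leaves calculations and data conventions to an SAP that is not shown, and with all treated subjects as denominator there would be no overstatement. This stands as a limit on the wording, but it does not dispose of the point. The no-imputation rule is unqualified, and counting a re-treated subject as a non-responder at later visits of the old cycle could be read as breaching it. The study-wide FAS is not a workable denominator for cycles 2 to 4, since it contains people who never entered them. Observed cases is the natural reading.

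**Not every relapsed subject leaves.** A reader might infer that all do. Those who decline, are ineligible, or have relapsed on one LCL side only stay in and count as non-responders. Only actual re-treatment removes anyone.

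**The at-rest endpoints differ.** Re-treatment depends on grade at maximum contraction, so a re-treated subject need not be a non-responder at rest. The argument is confined to grade 0/1.

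**Cycles counted per subject.** Re-treating one area would then also remove the other area, which may still be responding. In the Weibull case (median 20 weeks, areas assumed independent, u = 1), 10% of all subjects at Week 16 are excluded GL responders. The GL rate is nevertheless overstated, at 81% against 70%.

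**Redaction.** Part of the endpoint list and of the re-treatment criteria is blacked out. A time-to-event analysis may be there, so its absence cannot be asserted.

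**Weight.** The primary endpoints are safety (Section 2.1.1) and all analysis is descriptive (Section 9.1.6). No test or error rate is touched. This stands, and it lowers the severity.

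**Conclusion.** The concern holds in limited form. Read together, Sections 2.1.2, 6.1.6.3 and 9.1.3 and the Synopsis imply observed-case rates within cycle, with exit triggered by failure on the same scale. For the grade 0/1 endpoints, rates after cycle Week 12 in cycles started by study Week 28 are conditional on not having been re-treated and overstate persistence.

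Under the normal model with SD 5 weeks and half to all relapsed subjects re-treated, the excess at cycle Week 24 is about 9 to 19 points for a 5-month mean and about 4 to 9 points for 6 months. These sizes rest on the assumed distribution and re-treatment share. The direction needs only that some relapsed subjects are re-treated.

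The documents do not support the wider inference that efficacy results as a whole are unreliable: Day 7 through cycle Week 12 and all safety analyses are unaffected. Severity is moderate.

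**What to change.** Qualify Sections 2.1.2 and 9.1.3, and carry the same wording into the SAP:

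1. For the grade 0/1 endpoints after cycle Week 12, the denominator is all subjects treated in that area in that cycle whose planned follow-up reaches the visit. The follow-up condition is needed because late cycles run into the end of the study and Section 3 guarantees only 24 weeks for every subject.
2. A subject already re-treated in that area counts as a non-responder at the remaining visits of the earlier cycle. State that this is part of the endpoint definition and an exception to the no-imputation rule.
3. Print n at each visit and show the observed-case percentage beside the main figure, labelled as conditional on no re-treatment.
4. Add an estimate of time to loss of grade 0/1 by area and cycle (for example Kaplan-Meier), unless the redacted text already contains one.

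The re-treatment rule itself is not touched. The cost is some wording and a few extra tables, with no new data. Late-cycle percentages will look less favourable. Counting re-treatment as non-response is one choice of estimand among several, which is why the observed-case figures should stay visible.

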5.2.1 Inclusion Criteria

- 1. Male or female 18 years of age or older.
- 2. Moderate to severe GL (grade 2 or 3 on the 4-point Photographic Scale ranging from 0 [none] to 3 [severe]) at maximum frown as assessed by the Investigator (GL-ILA).
- 3. CCI
- Moderate to severe bilaterally symmetrical LCL (grade 2 or 3 on the 4-point Photographic Scale ranging from 0 [none] to 3 [severe]) at maximum smile as assessed by the Investigator live assessment (LCL-ILA).
- 5. CCI
- Female of non-childbearing potential (i.e., post-menopausal [absence of menstrual bleeding for 1 year prior to screening, without any other medical reason], or has undergone hysterectomy or bilateral oophorectomy).

OR

Female of childbearing potential with a negative urine pregnancy test at screening and baseline, and agrees to use a highly effective and approved contraceptive method for the duration of the study. A highly effective method of contraception is defined as:

Bilateral tubal ligation;

- Combined (estrogen and progesterone containing) oral, intravaginal or transdermal contraceptives that inhibit ovulation as the primary mode of action, on a stable dose for at least 28 days prior to screening visit;
- Intra uterine device (IUD) inserted at least 28 days prior to screening visit;
- Intrauterine hormone-releasing system;
- Partner vasectomized for at least three months prior to screening visit;
- Progestogen-only oral, injectable or implantable contraceptives that inhibit ovulation as the primary mode of action, on a stable dose for at least 28 days prior to screening visit; or
- Strict abstinence (i.e., refraining from heterosexual intercourse for the entire duration of the subject's participation in the study).
- 7. Time and ability to complete the study and comply with instructions.
- 8. Understands the study requirements and signed the informed consent form (ICF).

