7. CLINICAL STUDY ASSESSMENT

7.1 Efficacy Assessments

7.1.1 Investigator 4-point Photographic Scale of Glabellar Line Severity (GL-ILA)

The validated Investigator 4-point Photographic Scale of Glabellar Line Severity (GL-ILA) (Appendix 1) includes two grading systems: one for Investigator live assessments at maximum frown, and one for Investigator live assessments at rest. The scale represents the severity of glabellar lines from none (grade 0), mild (grade 1), moderate (grade 2) to severe glabellar lines (grade 3). Each grade is also depicted by an individual photograph and a descriptive text. The Investigators will be trained on the use of the 4-point Photographic Scale.

The Investigators will use the 4-point Photographic Scales for direct, live comparison with the subject's face at rest and maximum frown respectively, at screening, baseline (prior to treatment), and at all post-baseline visits (prior to treatment, as applicable).

	Title	Dec id
♣ GALDERMA	43QM1903 Clinical Study Protocol - QM1114 - LTS for LCL/GL	MA-40372

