7.1.3 Investigator 4-point Photographic Scale of Lateral Canthal Line Severity (LCL-ILA)

The validated Investigator 4-point Photographic Scale of Lateral Canthal Line Severity (LCL-ILA) (Appendix 2), developed by Galderma, includes two grading systems: one for the Investigator live assessments at maximum smile, and one for the Investigator live assessments at relaxed position. The scale represents LCL severities from none (grade 0), mild (grade 1), moderate (grade 2), to severe (grade 3). Each grade is also depicted by an individual photograph and descriptive text. The Investigators will be trained on the use of the LCL-ILA.

The Investigators will use the LCL-ILA for direct, live comparison with the subject's face for grading LCL severity at screening, baseline (prior to treatment), and at all post-treatment visits. Left and right LCL should be assessed separately at relaxed position and maximum smile.

CCI	
CCI	
CCI	
CCI	
CCI	

8-26 19:44

43QM1903 Clinical Study Protocol - QM1114 - LTS for LCL/GL

Doc id

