9.1.2.2 Full Analysis Set

The Full Analysis Set (FAS) includes all subjects who were administered the study product at least once and who have at least one post-baseline efficacy measurement. All efficacy variables will be analyzed based on the FAS.

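### The at-rest responder rates can include subjects with no lines at rest at baseline, who cannot respond; report the rate among those able to improve beside the FAS rate

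*Protocol*

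**What the plan says.** Section 2.1.2 of the protocol has two visible groups of secondary efficacy endpoints. The first is the share of subjects reaching grade 0 or 1 at maximum frown (GL) or maximum smile (LCL). The second, at issue here, is the share with "≥1 grade/level improvement from baseline at each visit in each treatment cycle using the" GL scale at rest and the LCL scale at relaxed position.

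Both scales run from 0 (none) to 3 (severe). For GL, section 7.1.1 describes two gradings: "one for Investigator live assessments at maximum frown, and one for Investigator live assessments at rest". For LCL, section 7.1.3 adds: "Left and right LCL should be assessed separately at relaxed position and maximum smile".

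The visible inclusion criteria in section 5.2.1 concern the contracted face only. For GL the requirement is "Moderate to severe GL (grade 2 or 3 on the 4-point Photographic Scale ranging from 0 [none] to 3 [severe]) at maximum frown"; for LCL it is grade 2 or 3, bilaterally symmetrical, "at maximum smile as assessed by the Investigator live assessment (LCL-ILA"). Sections 8.1.1 and 8.1.2 have the investigator grade both positions at screening and at baseline, but they state an inclusion threshold only for maximum contraction.

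The FAS (section 9.1.2.2) consists of subjects treated at least once with at least one post-baseline efficacy measurement. The same section states: "All efficacy variables will be analyzed based on the FAS".

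**The concern.** Grade 0 is the floor of the scale, so a subject who starts there at rest cannot improve by one grade. Nothing visible in the protocol keeps such a subject out of the trial, out of the FAS or out of this percentage. The reported rate is then the product of two things: how often treatment improves static lines, and how many subjects had static lines to begin with.

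The companion endpoint at maximum contraction is free of this. Entry at grade 2 or 3 means every subject can reach grade 0 or 1. The two endpoints will be read together, but only one of them can have a ceiling below 100%.

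The rates are to be given for each treatment cycle, and the objective is about repeated injections. Re-treatment depends on severity at maximum contraction (section 6.1.6.3), so the subjects contributing to a later cycle are a selected subset, and their share with baseline grade 0 at rest may differ from that of the first cycle. It may also differ between GL and LCL. A reader could take such a shift for a change or a difference in effect.

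**Working it through.** The protocol gives no at-rest response rate and no baseline distribution of rest grades, so there is no figure of its own to reproduce. The check is algebra with assumed inputs.

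**From the protocol:** scale floor of 0 (sections 7.1.1 and 7.1.3); response defined as an improvement of at least 1 grade (2.1.2); FAS without a rest-grade condition (9.1.2.2); about 900 subjects planned (9.2).

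**Assumed:** p0, the share of the analysed subjects at grade 0 at rest at baseline; and r, the response rate among those at grade 1 or higher.

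**Formulas.** Grade-0 subjects contribute no responders, so

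- reported rate = r × (1 − p0) + 0 × p0 = r × (1 − p0)
- ceiling (r = 100%) = 1 − p0
- shortfall against r = r × p0

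| Assumed p0 | Grade-0 subjects of 900 | Ceiling | Rate if r = 50% | Rate if r = 60% | Rate if r = 70% | Rate if r = 90% |
|---|---|---|---|---|---|---|
| 0% | 0 | 100% | 50% | 60% | 70% | 90% |
| 1% | 9 | 99% | 49.5% | 59.4% | 69.3% | 89.1% |
| 10% | 90 | 90% | 45% | 54% | 63% | 81% |
| 20% | 180 | 80% | 40% | 48% | 56% | 72% |
| 30% | 270 | 70% | 35% | 42% | 49% | 63% |

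Example: 0.60 × (1 − 0.20) = 0.48.

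**Will any such subject be present?** With independent subjects, the chance of at least one among 900 is 1 − (1 − p0)^900. This is 59% for p0 = 0.1% and 98.9% for p0 = 0.5%. Some grade-0 subjects are likely even if the share is very small. A share that small does not matter, however: at p0 = 1% the ceiling is still 99%.

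**Shift between cycles.** Hold r at 60%. If p0 is 30% among subjects in one cycle and 15% in a later one (both assumed), the reported rates are 0.60 × 0.70 = 42% and 0.60 × 0.85 = 51%. That is an apparent gain of 9 points with no change in effect among those able to improve. The same arithmetic applies to GL against LCL in one cycle.

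**The case against.** The strongest objection is that denominators for individual tables belong in the SAP, which is not at hand. Section 9.1 of the protocol does leave data conventions and calculations to it. The SAP may well add a restricted rate. But the protocol itself fixes the analysis set for every efficacy variable, and section 9.1 describes the SAP as elaborating what the protocol specifies. On the protocol's text, the rate is taken on the FAS. That grade-0 subjects count as non-responders is the natural reading of a percentage of subjects in that set, although no sentence says so expressly.

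Two inclusion criteria, next to those on GL and LCL severity, are redacted, as is text after the endpoint list. A rest-grade condition there cannot be ruled out. Against it, the readable investigator-assessment steps in sections 8.1.1 and 8.1.2 state an inclusion threshold for each scale and give none at rest. Some doubt remains.

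Little depends on the figure. The primary endpoints are safety, all analysis is descriptive (9.1.6), and the sample size has no statistical basis (9.2). No test or planned GL-to-LCL comparison uses the rate. This stands and limits the severity. It does not remove the point: in a single-arm study the percentage is itself the result, with no control arm under the same ceiling.

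The synopsis promises frequency tables by visit for categorical data. If these cover baseline rest grades, a reader can see p0. This helps, but it does not give the response rate among those able to improve.

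A reader might go further and infer that the FAS rate is biased downwards, or cannot be read as a response rate. The documents do not support either. For the quantity named, the percentage of FAS subjects who improve at rest, the proportion is valid. It is only lower than the rate in a different group, those with lines at rest.

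**Conclusion.** As the protocol reads, the at-rest responder rates are taken on a set that can include subjects with no possibility of response. If their share is p0, the ceiling is 1 − p0 and the rate is diluted to r × (1 − p0). For an assumed r of 60%, that is a loss of 6, 12 or 18 points at assumed p0 of 10%, 20% or 30%.

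The conclusion depends on p0 being above zero by a material amount. The protocol allows this but gives no figure, so it would be wrong to state as fact that the rate in this trial is capped appreciably below 100%. It also depends on the redacted criteria containing no rest-grade minimum and on the SAP not already restricting or supplementing the denominator.

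The FAS percentage should be kept. What is missing is the figure that separates effect from baseline rest grade and allows cycles and areas to be read against each other. Severity is minor: interpretation of a descriptive secondary endpoint.

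**What to change.** Add to section 2.1.2 or the SAP that each at-rest responder rate is reported in two ways:

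- on the FAS, as now;
- among FAS subjects with a baseline rest grade of at least 1 in the area concerned, by side for LCL, with that denominator stated for each visit and cycle.

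Beside these, show the number at baseline grade 0 at rest and the share of them who remain at 0.

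No new data are needed, because rest and relaxed grades are already recorded at baseline and at later visits. The cost is one sentence, about one extra row per table, and a smaller denominator, hence less precision, for the restricted rate.
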